4.3.2 Congenital anomalies registry

At periodic intervals after recruitment, the regional congenital anomalies register (CAR) and mortality register will be queried using the diagnostic codes for cardiac abnormalities. Information retrieved will include the baby date of birth, location, date and nature of the diagnosis, any known outcome, including death and the baby's NHS number. We will also collect details on the diagnosis of Down's syndrome or any other congenital anomaly. Other identification details will be stripped to enable data transfer compliant with the Data Protection Acts. This will be sent to the Study Office to be cross-referenced with the babies already on the study database, matching for Baby and Mother NHS numbers and baby date of birth. For those that match, diagnostic information will be transferred to the study database for analysis. Unmatched babies will either have been missed at study hospitals, been born at non-participating hospitals within the region or have been born outside the region. These figures will help inform the study of completeness of verification. Additionally, registry holders in adjacent regions (e.g. Mersey and Trent) will be asked to be vigilant for notification of CHD cases from the West Midlands region.

A similar process will occur at the Birmingham Children's Hospital, which is the tertiary referral centre for the entire region. As the study progresses, if it appears that not all cases are being collected through either of these two methods, regional primary care trusts may be approached to search their databases using diagnostic READ codes. This will be substantially more labour intensive, so methods to maximise identification of CHD through the CAR and Children's Hospital sources will be explored first.

4.4. Compliance and follow-up issues

The issues of compliance and follow-up in diagnostic accuracy studies are of a different nature to those of randomised trials of interventions. In the systematic review of PO as a screening tool, none of the studies reported specific problems about parental non-compliance, i.e. declining participation after having given consent to take part. The key issue for us is the timing of the PO test to avoid loss of participation after consent has been obtained. The study has been designed to tackle this issue by performing the test in the first few hours after birth, on admission to the postnatal ward, which has the added advantage of early detection of life-threatening cardiac disease prior to the onset of symptoms, a situation that can worsen the prognosis. Although it not possible to anticipate how many babies presenting late with CHD will not be captured by the study, it is not anticipated that this will be above 5%, given the measures described in section 4.3. This figure would be estimated from the number of mis-matches arising from the CAR and presented at the interim analysis to provide an opportunity to re-calculate sample size, if required.

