The participating centres have agreed to make it standard practice to perform PO within each unit and the clinical protocols changed accordingly. PO will be performed before 24 hours or discharge, preferably at around 3-6 hours of age which corresponds to admission to the postnatal ward. PO is routinely performed on babies on the Neonatal Unit. It is painless, extremely well tolerated by babies and requires minimal clinical training. It is estimated that to perform saturations on one hand and one foot will take no more than five minutes. The results of the PO will be recorded as percentage functional saturation for each limb. The date and time of testing will also be recorded. A cut off of <95% in either limb or a difference of $\geq 3\%$ between the limb readings will be considered to be abnormal. This threshold has been shown in previous studies to have the highest sensitivity. It also has the potential to detect coarctation of aorta, a treatable condition that has been missed in earlier studies with different thresholds (14,15) It is anticipated that the maximal sensitivity of the test is achieved by about 6-12 hours of age (9;14;15), by which time we anticipate the majority of babies in this study will have been screened. If PO is low and the clinical examination is unremarkable, the PO will be repeated 1-2 hours later for a definitive definition of abnormality. If the saturations remain low, oxygen will be administered (nitrogen washout or hyperoxia test) to identify potential respiratory causes for low saturations. An echocardiogram will be performed in all case of persisting low saturations (i.e. test positive cases)

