6. ACCRUAL AND ANALYSIS

6.1. Sample size

The approach used in the sample size calculations is to consider the power that a study of a certain size has for the lower limits of the confidence intervals for both sensitivity and specificity to exceed particular values (and hence prove that the test is statistically significantly superior to those values). Sample size computations have been undertaken assuming that the screening strategy will have a sensitivity of 75% and a specificity of 99.5%. Sample sizes for CHD prevalence between 2 and 5 per 1000 using a one-tailed significance level of 2.5% have been computed.

Simulations of the study design and analysis (using 10,000 repetitions) were performed to account for (1) sampling variability in the observed number of cases of CHD and (2) sampling variability in the observed sensitivity and specificity, and (3) to incorporate the use of binomial exact methods to estimate confidence intervals. Standard asymptotic sample size computations do not allow for all three of these issues to be considered simultaneously. Plots of power against the values of sensitivity and specificity that the study wishes to rule out were constructed for sample sizes of 10000, 15000, 20000, 25000, 30000 and 35000.

Based on these simulations it was observed that a sample size of 20,000 will have 80% power to demonstrate that sensitivity is above 61% at a prevalence of 5 per 1000 in the overall sample. For the subgroup of women who are not selectively screened antenatally, it is anticipated the prevalence to be around 2 per 1000, a level at which sensitivity of 52% can be detected with 80% power. If the sample size is increased to 25,000 the study will have 80% power to prove the sensitivity to be above 63% and 55% at 5 and 2 per 1000 CHD prevalences respectively; if it is increased to 30,000 the corresponding values are 64% and 57%. Variation of prevalence does not affect the power to detect differences in specificity. For sample sizes above 15,000 the study will have greater than 90% power to prove that the specificity is above 99.3%.

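### CHD cases missed among tested babies are all PO-negative, so the loss tolerated in section 4.4 biases sensitivity and NPV upward, and a sample-size recalculation cannot remove that bias

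*Protocol*

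**What the plan says.** Protocol section 4.4 concedes that some babies who present late with CHD will not be captured, and states that "it is not anticipated that this will be above 5%, given the measures described in section 4.3". The figure is to be estimated from mis-matches with the congenital anomaly register and "presented at the interim analysis to provide an opportunity to re-calculate sample size, if required".

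Verification depends on the test result (2.2): echocardiography for positives, follow-up for negatives. On positives, 4.1 says "An echocardiogram will be performed in all case of persisting low saturations (i.e. test positive cases". Section 4.3.2 describes the case finding for the rest: register and mortality queries, a similar process at the regional tertiary centre, alertness in adjacent registries, and a primary-care READ-code search if capture looks incomplete. Section 7.1.2 adds quarterly reports on completeness of verification.

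Section 5.1 discusses differential verification. It concludes that the predictive values escape bias, and that sensitivity and specificity escape difficulties of interpretation because both reference standards should find clinically significant CHD about equally well.

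Section 6.1 sizes the study on the power for the "lower limits of the confidence intervals for both sensitivity and specificity to exceed particular values", with sample sizes "using a one-tailed significance level of 2.5% have been computed". Its simulations allow for a random number of cases and for sampling variability in sensitivity and specificity, and use exact binomial intervals. Incomplete capture is not among the listed features.

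**The concern.** Recalculating the sample size suits loss at random, which costs precision only. The loss here is not random. A tested baby with CHD who is never found must have passed PO, so the only cases that can disappear are false negatives. Each one is removed from the sensitivity denominator and added to the true negatives.

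Sensitivity is the quantity that the study was sized to establish (5.1, 6.1), and NPV feeds the decision model. Both move in the favourable direction. Recruiting more babies leaves the shift in place and shrinks the interval around it. The sensitivity analyses that the protocol names do not reach the problem: 5.1 addresses spectrum composition, and 6.3 and 6.4 address listwise deletion of missing data. An uncaptured case is not missing data; it is recorded as disease-free. A tolerated miss on the follow-up side alone also sits badly with the claim in 5.1 that the two standards detect equally well.

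**Working it through.** **Inputs** (Protocol 6.1 and 4.4): sizing "assuming that the screening strategy will have a sensitivity of 75% and a specificity of 99.5"%; one-sided 2.5%; exact limits; 20,000 babies at 5/1000, about 100 cases; benchmark 61%; uncaptured at most 5%, denominator not stated.

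**Reproducing the plan.** Section 6.1 says "a sample size of 20,000 will have 80% power to demonstrate that sensitivity is above 61% at a prevalence of 5 per 1000". I let the number of cases n follow Binomial(N, prevalence), declare success when the one-sided 2.5% Clopper-Pearson lower limit exceeds the benchmark, and average over n. At a true 75% this gives 82.5% power for 61%; 62% would give 76.5%, so 61% is the highest whole percent with at least 80%. The other five sensitivity statements give 80.8% (52%), 79.7% (63%), 80.3% (55%), 80.7% (64%) and 79.8% (57%). The sizing is sound under full capture.

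**Shift in sensitivity.** Let s be true sensitivity and remove false negatives only.

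- 5% of all CHD cases: apparent value s/0.95. 0.75/0.95 = 78.9%; 0.61/0.95 = 64.2%.
- 5% of PO-negative cases: apparent value s/[s + 0.95(1 − s)]. 0.75/(0.75 + 0.2375) = 75.9%; 0.61/(0.61 + 0.3705) = 62.2%. At s = 61% this is 0.05 × 0.39 = 1.95% of all cases.
- 5% of late presenters, if half of the PO-negative cases are found early by other routes (my assumption): 0.05 × 0.5 × 0.39 ≈ 1% of all cases; 0.61/0.99 = 61.6%.

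**Shift in NPV.** At a true 75%, 100 cases give 25 false negatives. True negatives are 19,900 × 0.995 = 19,800.5, so 19,825.5 babies test negative. True NPV is 1 − 25/19,825.5 = 99.87%. With five false negatives lost it reads 1 − 20/19,825.5 = 99.90%. Missed cases per 1,000 negatives fall from 1.26 to 1.01.

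**Chance that the lower limit exceeds 61% when true sensitivity is exactly 61%** (5/1000; captured cases follow Binomial(N, 0.005 × (1 − fraction lost)) with the apparent sensitivity above):

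| Loss, all false negatives | 20,000 | 25,000 | 30,000 |
|---|---|---|---|
| None | 2.00% | 1.99% | 2.05% |
| 1% of all cases | 2.7% | 2.8% | 2.9% |
| 5% of PO-negative cases | 3.5% | 3.7% | 4.0% |
| 5% of all cases | 7.7% | 8.9% | 10.3% |

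The full-capture rate is below 2.5% because exact limits are conservative. If 5% of cases are lost at random, the rate at 20,000 stays at 2.0%, which confirms that the direction of the loss is what matters. In the 2/1000 subgroup with its 52% benchmark, the rate goes from 1.6% to 2.4% (5% of PO-negative cases) or 3.5% (5% of all cases).

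**The case against.** Four points can be made for the plan.

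1. A reader might infer that the error rate simply becomes about 8%. The text does not support that. Section 4.4 speaks of late presenters and gives no denominator. The 7.7% needs the full ceiling applied to all CHD cases, in the 5/1000 sample. Some PO-negative cases will be found early, through signs at examination (4.3.1) or because antenatally suspected babies go to a neonatal unit (3.1.3). The effect may then be close to the 2.7% row. This stands, and the size must be given as a range.

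2. A reader might infer that sample-size recalculation is the only response. It is not: 4.3.2 sets out several sources and an escalation step, and 7.1.2 has completeness reported. Better capture is the direct remedy. These steps reduce the loss, but none adjusts the estimate for what remains.

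3. Register mis-matches, as 4.3.2 describes them, are babies not on the study database: missed at study hospitals or born elsewhere. They cost precision only, and recalculation suits them. This stands. It also means that the mis-match count does not measure enrolled cases that no source finds, which are the ones that cause bias.

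4. A reader might infer that a declared 61% success rule is corrupted. No such rule exists. Sections 5.2 and 6.3 plan estimates with 95% intervals, and 61% is a sizing benchmark. On the estimation scale the shift is at most 3.9 points, against an exact interval of about 65% to 83% for 75 of 100 cases.

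It could also be said that a bounding analysis belongs in a SAP. But the protocol itself fixes a response in 4.4 and a reassurance in 5.1, and both need correcting there.

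**Conclusion.** The concern holds as a matter of bias with an uncertain and possibly small size. Among enrolled, tested babies, undetected CHD falls entirely on the PO-negative side, so sensitivity and NPV are overstated and enlarging the sample cannot correct this. At the stated ceiling, a true 75% reads as about 76% to 78.9%. The chance of the lower limit passing 61% when the truth is 61% is about 3.5% to 7.7% at 20,000 and 4.0% to 10.3% at 30,000, against about 2.0% with full capture (nominal 2.5%). If only about 1% of all cases are lost, it is about 2.7% at 20,000.

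These figures assume 5/1000, complete verification of test positives, and loss at the stated fraction. Which end of the range applies cannot be settled until the 5% has a denominator.

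**What to change.** - **4.4:** state whether the 5% refers to all CHD cases, PO-negative cases or late presenters. Separate enrolled but undetected cases (bias) from babies never enrolled (precision only). Keep sample-size recalculation for error in the assumed prevalence and for never-enrolled cases.
- **6.3:** beside the primary estimate, add a bounding analysis that recomputes sensitivity, NPV and their exact intervals with uncaptured enrolled cases returned as false negatives, once at the estimated fraction and once at the 5% ceiling. For example, 75 true positives among 95 captured cases give 78.9%; with 95/0.95 = 100 as denominator the bound is 75.0%. The estimated fraction needs a source other than the mis-match count.
- **5.1:** qualify the statement that the sensitivity estimate escapes difficulties of interpretation, and the matching one on predictive values, as conditional on complete capture among test negatives.

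The cost is one extra analysis on data already collected, with no change to care or follow-up. The downside is that the bound is conservative if capture is in fact complete: at a true 75% and 20,000 babies, the bounded lower limit would clear 61% only about 56% of the time, compared with 82.5% for the unadjusted limit. If 5% of all cases really are lost, it clears 61% about 84% of the time. It should therefore accompany the primary estimate and not replace it, and no new success threshold is needed.

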2.2. Overview

[figure not shown]

Figure 1: Flow chart of study organisation

This study will assess the accuracy, effectiveness and efficiency of PO in a delayed-type cross-sectional accuracy study. First, PO will be performed soon after delivery in all cases, which will have the advantage of identifying potentially serious low oxygen saturations in a timely fashion before symptoms are apparent. Integrating PO into the assessments performed routinely by the midwife when mother and baby are transferred from the delivery suite to the post-natal ward will make this design practicable and achieve maximum recruitment. Testing will occur early but over a range of times within the first 24 hours after birth (usually within 3-6 hours) or before discharge, allowing analysis of the optimum time for PO screening. After conducting PO, we will use different reference standards for test positive and test negative cases: echocardiography for the former and follow-up for the latter.

In this design, it would be unlikely that the subsequent clinical examination could be performed independently of the PO results, as midwives would want to alert the medical staff to a low saturation. This precludes a direct comparison of PO against clinical examination, as the latter would be prone to work-up bias. This comparison will be made through decision-analytic modelling using unblinded and historical data for input and appropriate sensitivity analyses conducted.

Clearly, in the presence of a feasible and accurate CHD screening strategy, there will be a need to consider the cost-effectiveness. The cost-effectiveness of PO in combination with postnatal clinical examination will be evaluated against examination alone and examination and antenatal screening, in a model-based analysis. Two systematic reviews of the performance of antenatal screening for CHD in first trimester (4) and second trimester (19) have been performed. Data on this group will be collected as part of our study. Using directly obtained information on outcomes and costs from a large number of babies in a real-life setting, the implications of all methods of identification of CHD will be modelled, thereby improving the generalisability of the results.

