2.5. Setting

The setting will be 6 large maternity units in the West Midlands region. These units are based in the following hospitals: Birmingham Women's, Heart of England, City (Birmingham), New Cross (Wolverhampton), University Hospital of Coventry & Warwickshire (Coventry), and Royal Shrewsbury. These units serve a large, socio-economically and ethnically diverse population, which will aid generalisability of findings and have a large total number of deliveries (over 30,000 per annum). The units also represent the spectrum of obstetric settings, from a busy district general hospital to a specialised tertiary referral centre.

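### Register mis-matches (section 4.4) cannot estimate the share of late-presenting CHD that follow-up fails to capture, because they count register cases outside the study

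*Protocol*

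**What the plan says.** Oximetry-positive and oximetry-negative babies are verified differently: "echocardiography for the former and follow-up for the latter" (section 2.2). Section 2.3 sets the reference standard as CHD identified up to one year.

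Section 4.4 takes up cases that present late and are not captured. It gives an expectation, "it is not anticipated that this will be above 5%, given the measures described in section 4.3", and then an estimator: "This figure would be estimated from the number of mis-matches arising from the CAR and presented at the interim analysis". The stated use is possible re-calculation of the sample size.

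Section 4.3.2 describes the matching. The register extract runs in one direction: "This will be sent to the Study Office to be cross-referenced with the babies already on the study database". Of those who fail to match it says: "Unmatched babies will either have been missed at study hospitals, been born at non-participating hospitals within the region", or born outside the region. It adds: "These figures will help inform the study of completeness of verification".

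Section 7.3 places the interim analysis 3-4 months into recruitment. Section 5.3.2.3 says false negatives are not definitively identified until the 12-month follow-up.

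**The concern.** The 5% expectation is justified by the measures in section 4.3, which is the reference-standard section. It is therefore about ascertainment: CHD that develops or declares itself in a study baby and is never found. The estimator offered for it counts something else, namely register cases for whom there is no study record.

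The error that matters is a study baby with a negative oximetry result and CHD that no source reports. That baby stays in the analysis as a true negative, so a false negative is lost and sensitivity rises. Improving the precision of the sensitivity estimate is a stated purpose of the study (section 5.1), and that section relies on clinically significant CHD being found about equally well under both reference standards. A completeness check that cannot see these babies could reassure the monitoring committee or alarm it, in either case for reasons unrelated to missed cases. The planned response, a larger sample, would not remove a bias of this kind.

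**Working it through.** **1. The plan's own figure.** Inputs from section 6.1: N = 20,000, prevalence 5 per 1000, sensitivity 75%, one-sided 2.5%, exact confidence limits, threshold 61%, stated power 80%. Taking cases as Binomial(20,000, 0.005), true positives as Binomial(cases, 0.75), and success as an exact lower limit above the threshold, full enumeration gives 82.5% power at 61% and 76.5% at 62%. So 61% is the highest whole-percent threshold with at least 80% power, and the plan's figure is reproduced to that rounding. The 5% non-capture figure has no stated derivation to reproduce.

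**2. Who can appear as a mis-match.**

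| Baby with CHD | In register | On study database | Result |
|---|---|---|---|
| Enrolled, register has the case | yes | yes | match |
| Not enrolled, or born elsewhere | yes | no | mis-match |
| Enrolled, register lacks the case | no | yes | nothing |

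The third row is the quantity wanted, and it contributes nothing to the count.

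**3. Does the count respond to missed cases?** Section 2.5 says the units "have a large total number of deliveries (over 30,000 per annum"), and the target is 20,000 in 12 months. Assume 30,000 births, hence 10,000 not enrolled; CHD at 5 per 1000 in both groups (50 and 100 cases); and the same register completeness c in both. The documents give no value for c, so a range is shown. Mis-matches from study units = 50c, matches = 100c, share unmatched = 50c/150c = 1/3. False negatives absent from the register = 25(1 − c). The last column takes the register as the only source for oximetry-negative babies, which is a worst case.

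| c | Mis-matches | Share unmatched | False negatives absent | Apparent sensitivity |
|---|---|---|---|---|
| 100% | 50 | 1/3 | 0 | 75.0% |
| 95% | 47.5 | 1/3 | 1.25 | 75.9% |
| 90% | 45 | 1/3 | 2.5 | 76.9% |
| 80% | 40 | 1/3 | 5 | 78.9% |

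The share does not move, and the count falls as more cases are missed.

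**4. Size of the bias.** Expected cases are 20,000 × 0.005 = 100: 75 true positives and 25 false negatives. Oximetry-positive babies have echocardiography, so losses are taken to fall on the 25. Apparent sensitivity = 75/(100 − missed).

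- 5% of 25 late presenters: missed 1.25; 75/98.75 = 75.9%.
- 10% of 25: missed 2.5; 75/97.5 = 76.9%.
- 5% of all 100 cases: missed 5; 75/95 = 78.9%.

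Negative predictive value: true negatives = 19,900 × 0.995 = 19,800.5, so 19,800.5/19,825.5 = 99.87%. With 1.25 cases moved it is 19,801.75/19,825.5 = 99.88%.

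**5. Effect on the test against 61%.** If true sensitivity were 61%, 39 of 100 cases would be oximetry-negative. Losing 5% of them (1.95) gives an apparent 61/98.05 = 62.2%. By the enumeration in step 1, with cases reduced accordingly, the chance of wrongly showing sensitivity above 61% goes from 2.0% to 3.5%. If 5% of all CHD were lost it would be 7.7%.

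**The case against.** **Other sources exist.** Sections 2.3 and 4.3.2 add the regional children's hospital, mortality sources, hospital information departments, adjacent registers and, if needed, primary care codes. Critical and serious CHD is largely defined by death or intervention, so most such cases should reach the tertiary centre or a mortality source. This stands, and it is a reason to expect few missed cases. It does not turn the mis-match count into an estimate of how many there are.

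**The term is loose.** Section 4.4 says mis-matches where section 4.3.2 says unmatched babies. If the former were meant to include CHD known to the study or the children's hospital but absent from the register, it would inform completeness. Section 4.3.2 describes only the other direction. A failed record link would also appear as a mis-match, but that is a case the register already holds.

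**Place of birth is retrieved.** Births elsewhere can therefore be separated. That is useful, but the one-third share in step 3 already concerns study-unit births only.

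**The interim is not the only look.** Registers are queried periodically, and completeness of verification is reported quarterly (section 7.1.2). This stands, but no other estimator is given for those reports.

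**Stronger readings a reader might infer.** One is that sensitivity would be overstated by 4 to 8 points. That applies 5% or 10% to all CHD, whereas section 4.4 speaks of late presenters, and the 10% is not in the protocol. Another is that the mis-match count decides whether primary care codes are searched. Section 4.3.2 ties that search to cases appearing to be missed by the register and the children's hospital, and names no such trigger.

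**Conclusion.** As sections 4.4 and 4.3.2 are written, the stated estimator targets non-enrolment and births elsewhere, not CHD missed among enrolled oximetry-negative babies, and it is read before any baby has reached the one-year horizon. That much follows from the text without numerical assumptions.

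The consequence is an unmeasured upward bias in sensitivity, probably of about 1 point at the protocol's cap and 2 points at twice the cap. This rests on 100 expected cases, true sensitivity of 75%, late presenters being the oximetry-negative cases, and the 5% applying to them. The 78.9% figure needs 5% of all CHD to be missed and is an outer bound rather than the expected size. The protocol does not show that ascertainment will be poor; it shows that the planned check could not tell.

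**What to change.** In section 4.4:

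- Keep mis-matches, split by place of birth, as a measure of uptake and linkage only.
- Once 12-month follow-up is complete, cross-classify CHD cases among enrolled oximetry-negative babies by source: anomaly register, regional children's hospital, mortality sources. Restrict this to oximetry-negative babies, because positives are found through echocardiography and have a different chance of capture.
- Estimate unascertained cases from the two-source overlap of register and children's hospital by Chapman's formula, (n₁ + 1)(n₂ + 1)/(m + 1) − 1, less the distinct cases already found. Here n₁ and n₂ are the cases in each source and m those in both. Cases found only through mortality sources are set against the estimate so that they are not counted twice.
- Report a sensitivity analysis that adds the estimated missed cases to the false negatives.

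The cost is one extra analysis on sources already being queried. Two limits should be stated beside it: with about 25 expected cases the estimate will be imprecise, and positive dependence between the sources makes it a lower bound. A third, deaths-only source in a log-linear model would be too sparse to help.
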